11.6.4 Progressive Disease (PD)

Either one of the following will define an overall response of PD:

- a. At least one response parameter including CT/MRI, MIBG, and/or bone marrow and/or FDG-PET response is PD. If PD is found by one parameter, the other two parameters are not required to be evaluated to define an overall response of PD.
- b. Treating physician grades patient as progressive disease based on clinical assessment without radiographic or bone marrow evaluations.

11.6.5 Stable disease (SD)

Response of stable disease for at least one parameter, with response of SD, NI, or SD-NTL for other parameters.

11.6.6 Minor response (MR)

Complete response, Complete-MRD response, and/or partial response for one parameter (i.e. CT/MRI, MIBG (FDG-PET if MIBG non-avid), bone marrow), with response of stable disease for second parameter and any response other than PD or inevaluable for third parameter.

11.6.7 Not evaluable (NE)

Response of Not evaluable for one or more response parameters including CT/MRI, MIBG (FDG-PET if MIBG non-avid), or bone marrow, unless one parameter that had measurable/evaluable tumor at study enrollment. However, if one parameter is done and demonstrates PD this is defined as an overall response of PD. In addition, response may be declared not evaluable if review by the Study Management Committee/PI deems that there is insufficient data to grade response

11.6.8 No Progression

Baseline status at enrollment was NI or non-target lesions only for CT, NI for bone marrow, NI for MIBG (FDG-PET if MIBG avid) and there has NOT been PD at any site since on protocol therapy.

11.6.9 Not done (ND)

Response was not assessed at this timepoint.

11.6.10 Summary

The overall response as assessed at any particular time point based on consideration of each of the three parameters as defined above is summarized in the following table:

Overall Response Assignment			
CT/MRI Response	MIBG Response	Bone Marrow Response	Overall Response
PD for any one parameter with any response (including Not Done or Inevaluable) for the other 2 parameters. PD may also be defined by clinical assessment of the treating physician only.			PD
CR	CR	CR	CR
CR for one parameter with either CR or NI for other parameters			CR
MIBG response= CR or NI CT/MRI response = CR or SD-No Target Lesions or NI		CR-MRD	CR-MRD
CR or PR or SD-No Target Lesions	PR	CR or CR-MRD or NI -OR- SD if $\leq 5\%$ tumor in bone marrow	PR
PR	CR or PR or NI	CR or CR-MRD or NI -OR- SD if $\leq 5\%$ tumor in bone marrow at study entry	PR
SD for one parameter, with SD or NI or SD-NL for other two parameters			SD
CR or CR-MRD or PR for at least one parameter, SD for a second parameter, and any response other than PD or Not Evaluable for other parameter			Minor Response
Response of Not Evaluable for any one of the 3 parameters that had measurable/evaluable tumor at study enrollment and no PD for any parameter.			Not Evaluable
No response evaluations performed for any of the 3 parameters			Not Done
NI or non-target lesions only at enrollment and no PD on subsequent timepoint	NI at enrollment and no PD at subsequent time point	NI at enrollment and no PD at subsequent time point	No Progression

*For patients who utilize FDG-PET in place of MIBG response, then substitute FDG-PET response for MIBG response in this table to define overall response.

12.0 ADVERSE EVENT REPORTING REQUIREMENTS

12.1 Purpose

Adverse event data collection and reporting, which are required as part of every clinical trial, are done to ensure the safety of patients enrolled in the studies as well as those who will enroll in future studies using similar agents. Adverse events are reported in a routine manner at scheduled times during a trial. (Please follow directions for routine reporting provided in the data collection packet for this protocol). Additionally, certain adverse events must be reported in an expedited manner to allow for timelier monitoring of patient safety and care. The following sections provide information about expedited reporting through the use of a written IND safety report (MedWatch) to the Food and Drug Administration (FDA).

An **adverse event** is defined as any unintended or abnormal clinical observation that is not of benefit to the patient. Either the condition was not present prior to exposure to test medication, or it has worsened in intensity or frequency following exposure to test medication. Adverse events will be graded according to the NCI Common Terminology Criteria for Adverse Events (CTCAE), Version 4. A copy of the CTCAEv4 can be downloaded from the CTEP home page (<http://ctep.cancer.gov>).

12.2 Expedited Adverse Event Reporting to the FDA

Per CFR 312.32 (c), the sponsor of the IND, [name], must notify the FDA and all participating investigators in a written IND safety report of any adverse experience **associated with use of the drug** that is **both serious and unexpected**. Each written notification shall be made as soon as possible, and in no event later than **15 calendar** days after the sponsor's initial receipt of the information. Each written notification may be submitted on FDA Form 3500A (MedWatch) or in a narrative format and must bear prominent identification of its contents, i.e., "IND Safety Report" with an associated 1571 form that will be consecutively numbered. Follow-up information to a safety report should be submitted as soon as the relevant information is available.

The sponsor must also notify FDA **by telephone** or by **facsimile** transmission of any **unexpected fatal or life-threatening experience associated with use of the drug** in the clinical studies conducted under the IND as soon as possible but in no event later than **7 calendar** days after initial receipt of the information.

Each telephone call or facsimile transmission to the FDA shall be transmitted to the FDA division that has responsibility for review of the IND. Following each facsimile transmission of an expedited adverse event report to the FDA, a hard copy version of the report shall be transmitted to the FDA division along with an amended 1571.

12.3 NANT Operations Center Role in Expedited Adverse Event Reporting to the FDA

For purposes of this protocol, the expedited adverse event reports will be submitted to the FDA as above by the NANT Operations Center on behalf of the IND sponsor, [name]. The NANT Operations Center will also disseminate all expedited adverse event reports with NANT investigators, DraxImage, NDP, and Merck. The IND sponsor, [name], has also delegated to the NANT Operations Center the telephone/facsimile FDA notification responsibilities for unexpected fatal or life-threatening experiences.

A cover letter to accompany expedited adverse event reports will be prepared by the NANT Operations Center in collaboration with the IND sponsor, [name]. Contents will include:

1. An assessment of the adverse event, its significance/relevance to the study, and impact on the risk/benefit ratio of the study.
2. A statement as to whether this adverse event has been reported previously, and if so, whether the frequency is considered unusually high.
3. A statement as to whether the protocol and/or informed consent should reflect changes in the potential risks involved.

All IND submissions will be maintained in a master file at the NANT Operations Center.

12.4 NANT Site Investigator Role in Expedited Adverse Event Reporting

For any serious adverse event, both expected and unexpected:

- Contact the Study Chairperson and the NANT Operations Center to alert them to the existence of the serious adverse event within 1 working day, or 24 hours, of learning of the event.
- Within 2 working days, or 48 hours, of learning of the event complete the NANT SAE form (see NANT website www.nant.org under protocol data forms/generic forms packet) and email to [contact].
- Follow-up information should be submitted as an amended NANT SAE report as soon as relevant information is available.

Copies of all serious adverse event reports will be kept on file in the NANT Operations Center

All NANT institutions are to file internal and external AE reports with their Institutional Review Boards according to local institutional policy.

12.5 Additional Adverse Event Reporting Requirements for Merck & Co, Jubilant DraxImage and NDP

12.5.1 Merck & Co

The NANT Operations Office will provide Merck & Co., Inc. (Attn: Worldwide Product Safety; [contact]) with copies of all serious adverse experiences within two working days for patients randomized to Arm C. Additionally, NANT has agreed to report any pregnancy occurring in association with use of vorinostat to Merck & Co., Inc. (Attn: Worldwide Product Safety; [contact]). Details of pregnancy outcomes will also be reported. Serious adverse experiences will be reported using MedWatch forms.

NANT will also provide Merck & Co., Inc. (Attn: Worldwide Product Safety; [contact]) with details of any vorinostat overdoses. For the purposes of this overdose reporting, a vorinostat overdose will be considered any of the following:

- Receipt of a duplicate dose on any protocol day;
- Receipt of more than 14 days of vorinostat therapy;
- Receipt of daily doses more than 30% higher than prescribed;
- Receipt of an absolute daily dose of more than 400 mg.

12.5.2 Jubilant DraxImage

The NANT Operations Office will provide Jubilant DraxImage, Inc with copies of all serious adverse experiences associated with DraxImage's MIBG product within two working days. Serious adverse experiences will be reported using MedWatch forms.

12.5.3 NDP

[name] is the IND holder for the use of NDP's MIBG product. The NANT Operations Office will provide [name] with copies of all serious adverse experiences associated with NDP's MIBG product within two working days. Serious adverse experiences will be reported using MedWatch forms.

12.5.4 Additional NANT Obligations

The NANT Operations Office will also provide Merck, Jubilant DraxImage and [name] with a copy of all FDA Annual Progress Reports and bi-annual study progress reports. FDA Annual Progress Reports will cross-reference the Merck, DraxImage and NDP Investigational Compound Number (IND) at the time of submission.

12.6 Definitions of Adverse Event Terminology

Adverse Event (AE): An adverse event means any untoward medical occurrence associated with the use of a drug in humans, whether or not considered drug related.

Suspected Adverse Reaction: Any adverse event for which there is a reasonable possibility that the drug caused the adverse event. Reasonable possibility means there is evidence to suggest a causal relationship between the drug and the adverse event.

Unexpected Adverse Event or Unexpected Suspected Adverse Reaction: An adverse event or suspected adverse reaction is considered “unexpected” if it is not listed in the investigator brochure or is not listed at the specificity or severity that has been observed; or, if an investigator brochure is not available, is not consistent with the risk information described in the general investigational plan.

Serious Adverse Events (SAE) or Serious Suspected Adverse Reactions: An adverse event or suspected adverse reaction is considered serious if, in the view of either the investigator or sponsor, it results in any of the following outcomes:

Death of Patient	An event that results in the death of a patient.
Life-Threatening	An event that, in the opinion of the investigator, would have resulted in immediate fatality if medical intervention had not been taken. This does not include an event that would have been fatal if it had occurred in a more severe form.
Hospitalization	An event that results in an admission to the hospital for any length of time. This does not include an emergency room visit or admission to an outpatient facility.
Prolongation of Hospitalization	An event that occurs while the study patient is hospitalized and prolongs the patient’s hospital stay.
Congenital Anomaly	An anomaly detected at or after birth or any anomaly that result in fetal loss.
Persistent or Significant Disability/Incapacity	An event that results in a condition that substantially interferes with the activities of daily living of a study patient. Disability is not intended to include experiences of relatively minor medical significance such as headache, nausea, vomiting, diarrhea, influenza, or accidental trauma (e.g., sprained ankle).
Important Medical Event Requiring Medical or Surgical Intervention to Prevent Serious Outcome	An important medical event that may not be immediately life-threatening or result in death or hospitalization, but based on medical judgment may jeopardize the patient and may require medical or surgical intervention to prevent any of the outcomes listed above (i.e., death of patient, life-threatening, hospitalization, prolongation of hospitalization, congenital anomaly, or persistent or significant disability/incapacity). Examples of such events include allergic bronchospasm requiring intensive treatment in an emergency room or at home, blood dyscrasias or convulsions that do not result in inpatient hospitalization, or the development of drug dependency or drug abuse.

12.7 Reporting Secondary AML/MDS or Any Other Second Malignancy

Within two working days of a diagnosis of AML/MDS or other secondary malignancy following treatment for cancer, submit the following to the NANT Operations Center:

- A completed NANT SAE Form
- A copy of the pathology report confirming the AML/MDS or other malignancy
- A copy of the cytogenetics report (if applicable)

The NANT Operations Center will report the secondary malignancy to the FDA via MedWatch form and to [name] (IND Sponsor), Draximage (if their product), NDP (if their product; via [name], IND holder for NDP’s MIBG product for use in neuroblastoma), and Merck (if on vorinostat arm of the trial). Reporting to Merck will be within two working days, as for any SAE.

13.0 RECORDS AND REPORTING

See separate Data Forms Packet which includes the data submission schedule in the members section on the NANT web site (www.NANT.org)

The following are required to be submitted for all patients entered:

1. Study case report forms, bone marrow reports (including aspirate and biopsy reports), and radiology reports (CT/MRI/MIBG scans). These forms and reports are faxed to the NANT Operations Center at [contact] or sent by email as electronic files to [contact] at the end of each course of therapy (day 43-50 evaluation).
2. For **all** patients on study, CT/MRI and MIBG scans done as baseline tumor evaluation at study entry are required to be submitted into the NANT PACS system or on CD for central review (after approval of NANT Operations Center). Bone marrow slides from study entry may also be requested at the discretion of the Operations Center.
3. For all patients the MIBG scans done at day 43-50 will also be submitted for central review. The MIBG scans should be submitted after day 43-50 evaluation. For patients who report a CR/PR/SD on CT/MRI, scans done at day 43-50 should be submitted for central review after day 43-50 evaluation. In questionable cases, the Operations Center may request CT/MRI scans for central review. It is preferable that scans be submitted electronically into the NANT PACS system. However, when this is not possible scans can be submitted on CD to NANT Operations Center.
4. For patients who report a CR or CR-MRD in bone marrow, bone marrow slides will be submitted from study entry and from day 43-50 evaluation, and from the second bone marrow confirming CR if applicable.

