10.3.2 Primary Response Endpoint and Additional Assessments of Treatment Effect

The primary endpoint and analysis will be objective tumor response after one course of therapy based on central review, for all eligible randomized patients who received any amount of ¹³¹I-MIBG (modified intent-to-treat analysis). Two secondary analyses will (a) include all eligible randomized patients and (b) only patients evaluable for response as defined in the paragraph above in section 10.3.1. Patients will undergo complete disease staging (¹²³I-MIBG diagnostic scan, bilateral bone marrow aspirate and biopsy, anatomic imaging with CT or MRI scan, and urine catecholamines) at baseline and then approximately 6 weeks following ¹³¹I-MIBG infusion. Response will be assessed according to NANT response criteria v1.1. These criteria are modified from the International Neuroblastoma Response Criteria¹¹² in that they utilize RECIST 1.1 criteria for measurable tumors¹¹³ and Curie score for MIBG scan response.¹⁰⁶ Patients with an institutional report of complete response, complete response-MRD, partial response, or stable disease will have their response centrally reviewed. An exact logistic regression analysis will be used to compare the 3 arms in terms of response, while controlling for the stratification variables.

For the subset of patients receiving a second course of therapy (enrolled prior to Amendment 7A), the response to the second course of therapy will be reported as well as the overall response to two courses of protocol therapy. Response to the first course will nevertheless be the primary endpoint for study.

Additional endpoints for response to treatment will include response at each site of disease: bone marrow; soft-tissue sites; and ¹²³I-MIBG using NANT response criteria. Progression-free survival and overall survival (summarized with Kaplan-Meier plots) will be additional secondary endpoints.

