11.0 NANT RESPONSE CRITERIA v 1.2

Below are the NANT Response Criteria. Since patients on this study must have MIBG avid tumors, any reference to MIBG non-avid tumors is not applicable.

Overall response will incorporate all three parameters: CT/MRI, MIBG (FDG-PET is substituted for MIBG non-avid tumors), and bone marrow response with overall response defined as outlined in Section 11.6. Response for each parameter and overall response will be reported by the treating site using the criteria below. However, the final statistical analysis of response will utilize responses as graded by central review, using the same criteria below.

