11.6.3 Partial Response (PR)

Response of PR in both CT/MRI and MIBG (FDG-PET scan if tumor is not MIBG avid); or response of PR in either CT/MRI or MIBG (FDG-PET if MIBG non-avid) with response of CR, NI, or SD-NTL for other parameter or response of CR for MIBG with SD-NTL for CT response. Bone marrow response of either CR, CR-MRD, NI, or SD for patients with maximum amount of tumor $\leq 5\%$ at that given time point.

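### For site responders graded NI on CT/MRI, or NI or low-tumor SD in marrow, Section 13 does not routinely collect the material that central review of the primary endpoint needs

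*Combined protocol and SAP*

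**What the plan says.** Section 10.3.2 defines the endpoint: "The primary endpoint and analysis will be objective tumor response after one course of therapy based on central review". Section 10.1 selects the winner on the same centrally reviewed rate, and Section 11.0 adds that "the final statistical analysis of response will utilize responses as graded by central review". Section 10.3.2 also says who is reviewed: "Patients with an institutional report of complete response, complete response-MRD, partial response, or stable disease will have their response centrally reviewed".

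Section 13.0 governs what is sent in:

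- Item 1: case report forms and written marrow and radiology reports, for all patients.
- Item 2: baseline CT/MRI and MIBG scans, for all patients. Study-entry marrow slides may be requested at the Operations Center's discretion.
- Item 3, MIBG: "For all patients the MIBG scans done at day 43-50 will also be submitted for central review".
- Item 3, CT/MRI: "For patients who report a CR/PR/SD on CT/MRI, scans done at day 43-50 should be submitted for central review after day 43-50 evaluation". There is also a discretionary route: "In questionable cases, the Operations Center may request CT/MRI scans for central review".
- Item 4, marrow: "For patients who report a CR or CR-MRD in bone marrow, bone marrow slides will be submitted from study entry", together with the Day 43-50 slides.

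The response rules are wider than these triggers. Under 11.6.1 an overall CR accepts NI for CT/MRI and for marrow. Under 11.6.3 a PR on MIBG or CT/MRI may stand "with response of CR, NI, or SD-NTL for other parameter". The same paragraph accepts marrow NI, or marrow SD when tumor is at most 5%.

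**The concern.** The endpoint is central, but the submission rule depends on the site's component grade. Two grades compatible with an overall response, CT/MRI NI and marrow NI, trigger no routine follow-up submission for that component. For a PR, marrow SD with at most 5% tumor is a third. The treating site, which knows the arm, then supplies a grade that the central reader can compare with the written report but not with images or slides.

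Marrow SD is the sharpest case. With an otherwise qualifying MIBG and CT/MRI result, SD at or below 5% gives PR, a responder. SD above 5% gives Minor Response under 11.6.6, which 10.3.1 classes as a non-responder. The 5% reading decides the primary endpoint, and no slides are required there.

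For CT/MRI NI, a new lesion without MIBG uptake counts as progression under 11.1.4.3, and the central MIBG read would not show it.

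The winner is the arm with the highest observed rate, with no significance threshold. One patient in 35 is 1/35 = 2.9 percentage points.

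**Working it through.** **1. The plan's own figure.** Section 10.5 states an 80% chance of correct selection with 35 per arm and a best arm 15 points ahead. Let f and F be the binomial(35, p) mass and distribution functions for an inferior arm, and g the mass function for the best arm at p + 0.15. With ties broken at random and no interim looks:

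PCS = Σ g(x) · [F(x−1)² + F(x−1)·f(x) + f(x)²/3]

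The minimum over p is at about 0.43. It is 82.6% with random tie-breaking, and 79.4% if ties count as failures (first term only). The 80% reproduces, and it does not depend on the submission rules.

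**2. Responder patterns, by the text of 11.6.1 to 11.6.3.** All patients are MIBG-avid at entry, so MIBG is CR or PR in every responder.

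| MIBG | CT/MRI | Marrow grades accepted | Patterns |
|---|---|---|---|
| CR | CR or NI | CR, NI (overall CR) | 2 × 2 = 4 |
| CR | CR or NI | CR-MRD (overall CR-MRD) | 2 × 1 = 2 |
| CR | PR or SD-NTL | CR, CR-MRD, NI, SD ≤5% (PR) | 2 × 4 = 8 |
| PR | CR, PR, SD-NTL or NI | CR, CR-MRD, NI, SD ≤5% (PR) | 4 × 4 = 16 |

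Total: 4 + 2 + 8 + 16 = 30.

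**3. What Section 13 leaves out.** Marrow slides are not required when marrow is NI (8 patterns) or SD ≤5% (6 patterns), so 14. Follow-up CT/MRI is not required when CT/MRI is NI (7). If the trigger word SD excludes SD-NTL, 8 more patterns are added, giving 15.

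| | SD includes SD-NTL | SD excludes SD-NTL |
|---|---|---|
| CT/MRI not required | 7 | 15 |
| Marrow slides not required | 14 | 14 |
| Both not required | 3 | 7 |
| At least one not required | 7 + 14 − 3 = 18 | 15 + 14 − 7 = 22 |
| Both submitted | 12 | 8 |

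The summary table in 11.6.10 is not identical to the text: it does not list CT/MRI NI beside MIBG PR, and one PR row ties the 5% limit to study entry rather than to the time point assessed. The count follows the text.

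**4. From patterns to patients.** Let a be the share of responders with CT/MRI NI, and b the share with marrow NI or SD ≤5%. If the two are independent, the affected share is 1 − (1 − a)(1 − b). Neither a nor b is in the documents, so both are assumptions:

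- a = b = 0.1: 19%
- a = b = 0.2: 36%
- a = b = 0.3: 51%
- a = b = 0.4: 64%
- a = 0.5, b = 0.6: 80%

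With a = b, the share passes one half at about 0.29.

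**5. Sensitivity of the selection to one misgrade** (35 per arm, two equal inferior arms, no interim looks, random ties).

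| Inferior rate, lead | No error | One false responder in an inferior arm | In a random arm |
|---|---|---|---|
| 0.20, +0.10 | 0.736 | 0.679 | 0.727 |
| 0.30, +0.10 | 0.702 | 0.648 | 0.695 |
| 0.20, +0.15 | 0.867 | 0.829 | not needed here |

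The random-arm value for the first row is (2 × 0.679 + 0.822)/3 = 0.727, where 0.822 is correct selection when the false responder falls in the best arm. One false responder in each arm changes nothing.

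**The case against.** The strongest answer is that central review is not empty for these patients. Baseline scans, Day 43-50 MIBG scans and all written reports come in for everyone. New MIBG-avid lesions are progression, so the central MIBG read covers much of what a CT/MRI could add in avid disease. Section 11.2.5 itself judges marrow adequacy on the local pathology report. Section 10.3.2 commits to central review of every site CR, CR-MRD, PR or SD, and 10.1.1 bars a final decision at the second interim until that review is complete. Section 13 also points to a separate Data Forms Packet with the submission schedule, which may ask for more.

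Much of this stands, and it limits the point. A reader might infer any of the following, none of which the documents support:

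- *Most site responders cannot be graded centrally.* No patient shares are given, and the range in step 4 runs from 19% to 80%. The components can be graded from reports; they are not routinely gradable from source material.
- *Two of the three components go unchecked on most routes to response.* Both are missing in only 3 or 7 of 30 patterns.
- *Patients with only non-target CT/MRI lesions are excluded.* Section 11.1.4.5 names that grade as a form of stable disease, so this is an ambiguity.
- *Follow-up marrow slides may not be requested.* Section 13 is silent on that; it does not forbid it.
- *Any marrow that turns positive overturns a PR.* Under 11.2.3 and 11.6.3, tumor up to 5% still permits PR.
- *The loss in correct selection measures bias from Section 13.* It assumes one certain error in an inferior arm. The documents give no error rate, and an error in the best arm moves the figure up.

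What the objection does not remove is the mismatch. Written reports are the site's own reading. Section 11.2 says central marrow review is done on biopsies, and 11.1.4.8 has the central reviewer judge scan quality. Both need the material. The request for questionable cases is undefined, covers CT/MRI only, and is made by the office that assigns the arm.

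**Conclusion.** The point holds as an inconsistency between Section 13 and the endpoint in 10.1, 10.3.2 and 11.0. For site responders with CT/MRI NI, or with marrow NI or (for PR) SD at most 5%, the stated rule does not routinely bring in the Day 43-50 CT/MRI or the marrow slides. At least one item is missing in 18 of 30 responder patterns (22 if SD excludes SD-NTL), and both in 3 (or 7).

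The counts are unweighted and rest on the text of 11.6.1 to 11.6.3. How many patients are affected cannot be stated from the documents, and the conclusion is conditional on the Data Forms Packet not asking for more. The selection figures show only that one misgrade can matter at 35 per arm; they do not estimate a bias. The change should be made because the gap touches the primary endpoint and closing it is cheap.

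**What to change.** Align Section 13 with 10.3.2.

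- **Item 3:** submit the Day 43-50 CT/MRI for every patient whose site overall response 10.3.2 sends to central review, whatever the site's CT/MRI grade. State explicitly that NI and SD-NTL are included.
- **Item 4:** submit study-entry and Day 43-50 marrow slides for every patient with a site overall CR, CR-MRD or PR, including marrow NI and SD with at most 5% tumor.
- Keep the discretionary request for questionable cases as an addition, and make the Data Forms Packet agree.

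The cost is protocol wording, more scan uploads and slide shipments, and more reading time for the existing central reviewers. There is no new patient procedure, because Section 7.1 already requires Day 43-50 CT/MRI and bilateral marrows in all patients, even if negative at entry. Neither the sample size nor the design's selection probability changes.
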